## **7.4. Dosage Modification**

The doses may be titrated by 2 to 4 units once or twice in a week until FBG levels are lowered to <100 mg/dL (5.6 mmol/L) as tabulated in [Table ABEX.4](#).

Investigators will be trained to assess when they need to intervene the treatment regimen of subjects who do not reach glycemic targets. If any of the FBG values for 2 consecutive weeks exceed the limits outlined below with no other possible cause of hyperglycemia, rescue medication (more OAMs or GLP-1 RA or bolus insulin; switching to a different basal insulin is not permitted as decided by the investigator) will be prescribed in addition to the ongoing treatment.

- FBG >270 mg/dL (>15.0 mmol/L) from baseline to Week 6 (4 values/week)
- FBG >240 mg/dL (>13.3 mmol/L) from Week 6 to Week 12 (4 values/week)
- FBG >200 mg/dL (>11.1 mmol/L) from Week 12 to end of trial (4 values/week)
- HbA1c  $\geq 8.5\%$  ( $\geq 69.4$  mmol/mol) by and after Week 24

The dose and name of rescue medication must be properly documented in the eCRF. Subjects who had to use rescue medication during the study period will be excluded from the per protocol set (PPS) population.

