## 8.2. Discontinuation from the Study

Subjects will be discontinued from the study in the following circumstances:

- enrollment in any other clinical study involving an investigational product or enrollment in any other type of medical research judged not to be scientifically or medically compatible with this study
- participation in the study needs to be stopped for medical, safety, regulatory, or other reasons consistent with applicable laws, regulations, and good clinical practice
- investigator decision
  - the investigator decides that the subject should be discontinued from the study
  - if the subject, for any reason, requires treatment with another therapeutic agent that has been demonstrated to be effective for treatment of the study indication, discontinuation from the study occurs prior to introduction of the new agent
  - if the subject has persistent hypoglycemia or increased risk of hypoglycemia
- subject decision
  - the subject or the subject's designee requests to be withdrawn from the study

Subjects discontinuing from the study prematurely for any reason should complete AEs and other safety follow-up per Section 2 (Schedule of Activities), Section 9.2 (Adverse Events), and Section 9.4 (Safety) of this protocol.

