### 10.2. Populations for Analyses

For purposes of analysis, the following populations are defined:

Population	Description
Enrolled	All participants who sign informed consent form
Full Analysis Set (FAS)	All enrolled participants who take at least 1 dose of study treatment
Safety	Identical to FAS, as no randomization occurs (single arm trial)
Per Protocol Set (PPS)	All FAS subjects, who also meet the following criteria: a) have no violations of inclusion/exclusion criteria b) have not discontinued from the study prior to 24 weeks c) have not been off study medication for more than 14 consecutive days during the treatment period d) have not received chronic (lasting longer than 14 consecutive days) systemic glucocorticoid therapy (excluding topical, intra-articular, intra-ocular, and inhaled preparations)

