- All vital signs should be recorded in the subject in a resting state. If there is a suspicion of postural hypotension or autonomic instability, the investigators at their discretion might decide to record the blood pressure in a supine state and then after standing for 2 minutes to detect any postural hypotension. Blood pressure measurements should be done in the left arm with sphygmomanometer held at the level of the heart. Blood pressure recording in both arms is at the investigators' discretion in selective cases of pulse volume inequality or pulse being absent in either of the arms.
- Subjects will be instructed to daily measure the FBG levels mandatorily using glucometer before the morning meal till Week 12 and record in the subject diary. Also, subjects will be instructed to measure and record the blood glucose levels using glucometer if they have symptoms of hypoglycemia (including nocturnal hypoglycemia) at any time of the day or night.
- 1. Subjects will be instructed to perform 7-point SMBG level monitoring (glucose measurements before breakfast, lunch, and dinner; 2 hours after breakfast, lunch, and dinner; and at 3 am [± 1 hour]) 2-3 days in the week prior to Visits 2, 3, 4, 5, and 8, and record the values in the subject diary. Subjects will be instructed to carry the glucometers to the sites on Visits 3, 4, 5, and 8.
- . Subjects will be instructed to record the actual time and dose of Basaglar administration in the subject diary.

5. Changes/deviations from the planned analysis

Any deviation in implementing original statistical plan will be described and justified in the final clinical study report.

6. Analysis populations

Agreement and authorization of participants included/excluded from each analysis population will be reached prior to final database hard lock. Sponsor will supply a list of all participants to be excluded from the relevant analysis populations, including the reason(s) for exclusion from the analysis populations.

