6.3 Per-Protocol Analysis Set (PPS)

This analysis population will include all FAS subjects, who also meet the following criteria:

- a) Have no violations of inclusion/exclusion criteria
- b) Have not discontinued from the study prior to 24 weeks
- c) Have not been off study medication for more than 14 consecutive days during the treatment period
- d) Have not received chronic (lasting longer than 14 consecutive days) systemic glucocorticoid therapy (excluding topical, intra-articular, intra-ocular, and inhaled preparations)
 - Set to 'Y' if
 1. For all FAS subjects = "Y" and

- Date of completion/discontinuation is not less than date of visit 8 (week 24)
- 3. within a subject there is no DV.DVCAT = "MAJOR"

CONFIDENTIAL CS.BS.01.00 TPL-1.0: Statistical Analysis Plan Template

Page 19 of 85

7. General considerations

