15.1 Variables and derivations

In eCRF "Concomitant Medications: General Use" form we are capturing the concomitant medication related data.

Concomitant medications are defined as any medication taken after first administration of the IMP till the end of the trial.

All medications will be coded using the WHO-DD, dated (refer to DMP for dictionary date) All concomitant therapies that was originally mapped using the WHO Drug Dictionary in the ClinTrial database will be further classified using Anatomical Therapeutic Chemical (ATC) codes for reporting purposes.

The following parameters will be summarised separately for the subject's with concomitant medication and Special Interest Hyperglycaemia related concomitant medication:

- Number of subjects with at least one concomitant medication and Special Interest Hyperglycaemia related concomitant medication
- Number of subjects for each concomitant medication and Special Interest Hyperglycaemia related concomitant medication by ATC and PT.

The following variables will be listed concomitant and other medications:

- Subject Number
- Medication class/ Standardized medication name/ Reported term
- Dose and unit
- Frequency
- Route
- Start date of medication
- End date of medication

Rescue Medication:

The rescue medication related data will be captured in "Concomitant Therapy: Special Interest Hyperglycaemia" special form in eCRF.

The rescue medication we will identify using following variables:

- Date of first dose administration
- First Rescue medication date

Derivations:

All concomitant medication and Special Interest Hyperglycaemia related concomitant medication, which are identifies as follows:

 If start date of concomitant medication >= Date of first dose administration, then we will consider it as "concomitant medication".

For identification of rescue medication visit wise we will use the following derivation:

(First Rescue Medication Date – Date of First Dose Administration) +1

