15.2 Analysis

| Population: | FAS and PPS |
|-----------------|--|
| Stratification: | Table: by ATC and PT |
| | Listing: By subject |
| Statistics: | Concomitant medication and Special Interest |
| | Hyperglycaemia related concomitant medication will be |
| | summarized separately as (frequency, percentages) for |
| | table and listing will be presented for concomitant |
| | medication and Special Interest Hyperglycaemia related |
| | concomitant medication. |
| | The rescue medication will be summarized as (frequency |
| | and percentage) by visit (i.e. Week 4, 8, 12, 16, 20 and 24) |
| | for FAS population. |
| | By using formula mentioned in derivation section for rescue |
| | medication, we will get the Day at which the rescue |
| | medication will be started per subject, then we will convert |
| | these days to respective visits. |

e.g. if, subject in the trial who needs rescue medication on day 30 (Day 30 is calculated using derivation mentioned above for rescue medication) then this subject will be counted under week 4 visit (as Day 30 comes under the week 0 to week 4 visit).

Denominators for "n" are per visit, for "n-cumulative" it will be the number of subjects with at least 1 visit up to respective visit.

16. Adverse events

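### Protocol 7.4 bars rescued subjects from the per-protocol set but protocol 10.2 and SAP 6.3 do not, and SAP 20.1.4 blanks HbA1c without checking whether the sample came before rescue

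*Protocol*

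**What the plan says.** **PPS membership**

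- Protocol 7.4, after listing the rescue limits: "Subjects who had to use rescue medication during the study period will be excluded from the per protocol set (PPS) population". Rescue (more OAMs, a GLP-1 RA or bolus insulin) is added to ongoing treatment. The last limit listed is an HbA1c of at least 8.5%, dated "mmol/mol) by and after Week 24".
- Protocol 10.2 defines the PPS as "All FAS subjects, who also meet the following criteria" and gives four: no eligibility violation, no discontinuation before 24 weeks, no more than 14 consecutive days off drug, and no chronic systemic glucocorticoid. Rescue is not among them.
- SAP 6.3 repeats those four and programs membership as FAS, "Date of completion/discontinuation is not less than date of visit 8 (week 24"), and no deviation coded as major.
- SAP 6: "Sponsor will supply a list of all participants to be excluded from the relevant analysis populations", with reasons, before the hard lock. It names no criterion.
- Protocol 8.2 says that when a subject needs another effective agent, "discontinuation from the study occurs prior to introduction of the new agent".
- SAP 15.2 summarises rescue "by visit (i.e. Week 4, 8, 12, 16, 20 and 24") for the FAS. SAP 15.1 lists "First Rescue medication date" as an available variable.

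**HbA1c after rescue**

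- Protocol 10.3.3.1 and SAP 8.2 point 2 treat as missing only values recorded after the first rescue administration.
- In SAP 20.1.4, one bullet sets HbA1c to missing if the rescue start date is later than the first dose date. The next bullet, on LOCF, does compare the rescue start with the Week 24 collection date.
- SAP 20.1.6 (FBG) and 20.1.8 (7-point SMBG) repeat the first-dose wording.

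**The concern.** The PPS is the set for the planned repeats of the hypoglycaemia, HbA1c and HbA1c-target analyses. If its programmed rule omits an exclusion that the protocol states outright, the delivered tables will include subjects on added glucose-lowering agents, possibly bolus insulin, whom the protocol says are out. Whether they are removed would then depend on a list or a deviation code for which no rescue criterion is written.

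The 20.1.4 bullet reaches further, because it governs the FAS as well. Rescue will normally start after the first dose, so a test against the first dose alone is met by almost every rescued subject at every visit. Values taken before rescue would then be lost, although the protocol keeps them.

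**Working it through.** **1. The PPS rules side by side**

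| Source | Rescue criterion |
|---|---|
| Protocol 7.4 | Any use in the study period excludes |
| Protocol 10.2, a to d | None |
| SAP 6.3, a to d | None |
| SAP 6.3, programmed rule | None; major deviations only |

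Protocol 7.4 directs rescue as treatment, and neither document calls it a deviation, so the major-deviation flag does not catch it by definition. The rules give the same set only if nobody is rescued or every rescued subject already fails another criterion.

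**2. Size of the membership difference**

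The plan's own precision figure reproduces. For 11% and n = 200, 1.96 × √(0.11 × 0.89 / 200) = 4.34 percentage points; Table ABEX.3 gives 4.3.

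The documents give no rescue rate. Assume that 5% to 30% of 200 completers are rescued and meet every other PPS criterion:

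- 5%: 200 × 0.05 = 10 subjects differ; n = 190, half-width 4.45 points.
- 30%: 200 × 0.30 = 60 subjects differ; n = 140, half-width 5.18 points.

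These use the protocol's normal approximation. The loss of precision is modest; the main issue is who is in the set.

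**3. SAP 20.1.4 taken literally**

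SAP Table 7.1 puts Week 12 at day 84 and Week 24 at day 168.

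| First rescue | Protocol 10.3.3.1 and SAP 8.2 | SAP 20.1.4 bullet, literal |
|---|---|---|
| Before the Week 12 sample | Both values missing | Both values missing |
| Between the two samples | Keep Week 12; Week 24 missing | Both values missing |
| After the Week 24 sample | Keep both | Both values missing |

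In the second row, LOCF should carry the Week 12 value to Week 24. If the blanking is applied first, only baseline remains and the change becomes zero. In the third row two valid values are lost.

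The timing of rescue is not given. On the range in step 2, and with all rescue before the Week 24 sample, the loss runs from no valid values (all rescue before the Week 12 sample) to one Week 12 value for each of the 10 to 60 rescued completers (all rescue between the samples).

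**4. The conditional Week 24 route**

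If 7.4 is applied as worded, a subject who meets the 8.5% limit at Visit 8 and starts rescue before the Week 28 visit would leave the PPS because of that value. Every input here is assumed:

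- Week 24 HbA1c normal, mean 7.5%, SD 1.0.
- A quarter of those at or above 8.5% already rescued before Visit 8, and so excluded both under 7.4 and under a rule cut off at Visit 8.
- A share u of the rest starts rescue after Visit 8, unrelated to the exact value.

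Share at or above 8.5%: p = 1 − Φ(1) = 0.1587, about 32 of 200. Mean in that group: 7.5 + φ(1)/p = 9.025. With a fraction f = 0.25 + 0.75u of the group removed, the PPS mean is (7.5 − f·p·9.025)/(1 − f·p).

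| u | f | PPS mean | Shift from u = 0 |
|---|---|---|---|
| 0 | 0.25 | 7.437 | 0 |
| 10% | 0.325 | 7.417 | −0.020 |
| 25% | 0.4375 | 7.386 | −0.051 |
| 50% | 0.625 | 7.332 | −0.105 |
| 100% | 1 | 7.212 | −0.225 |

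Over means 7.2 to 7.8 and SDs 0.8 to 1.2, the shift is −0.007 to −0.036 at 10% uptake, −0.03 to −0.20 at 50%, and −0.07 to −0.45 at the 100% bound. Under protocol 10.2 and SAP 6.3 as listed, it is zero.

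**The case against.** **The two protocol sections can be read together.** Criteria a to d plus the 7.4 exclusion make one set, the SAP is based on that protocol, and the sponsor's list can apply it before lock. This stands as far as the protocol's intent goes, and it rules out saying that membership is unknowable. It does not repair SAP 6.3: the programmed rule still lacks the exclusion, and the list states no rescue criterion.

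**Protocol 8.2 would discontinue such subjects anyway.** They would then fail criterion b before Week 24. But 7.4 adds rescue to continuing treatment, and the SAP tabulates rescue by visit and has LOCF rules for post-rescue samples, so it expects these subjects to stay. This is a further inconsistency and does not settle the matter.

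**The SAP states the HbA1c rule correctly elsewhere.** SAP 8.2 point 2 is right, the neighbouring LOCF bullet compares dates, and SAP 20.2.4 asks for a listing flag on post-rescue results. The intent is therefore clear. The faulty bullet is still the derivation that a programmer would code.

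**Stronger readings that a reader might infer:**

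- *That the Week 24 HbA1c decides PPS membership.* Only 7.4 as worded allows it. Study Basaglar ends at Week 24, 8.2 points away from adding agents within the study, and SAP 15.2 counts rescue only to Week 24. No dated membership rule excludes the route, so it is possible but not established.
- *That PPS target attainment would be inflated.* Protocol 10.3.3.2 and SAP 8.2 give the denominator as the total FAS. A general SAP default uses the relevant population, so the text is ambiguous and no gain can be claimed.
- *That removing subjects rescued before Visit 8 would improve the PPS mean by a calculable amount.* Their Week 24 values are set to missing, or replaced by earlier ones under LOCF, so a calculation on Week 24 values fits neither table.

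**Conclusion.** The point holds on the text in two parts. The SAP as programmed keeps rescued subjects in the PPS, contrary to protocol 7.4, unless a route with no written rescue criterion removes them. The SAP 20.1.4 bullet contradicts protocol 10.3.3.1 and SAP 8.2 point 2; the wording in 20.1.6 and 20.1.8 has the same fault.

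Neither part needs an assumption; their size does. The difference of 10 to 60 subjects rests on an assumed rescue share of 5% to 30%. The HbA1c shifts for the Week 24 route illustrate a conditional reading and are not an estimate of bias.

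The membership problem touches only the supportive PPS repeats. The derivation problem also reaches the secondary HbA1c, FBG and SMBG analyses in the FAS. The FAS analysis of the primary hypoglycaemia endpoint is untouched. Both parts should be corrected before the populations are agreed; neither threatens the main conclusion.

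**What to change.** 1. Put one criterion in protocol 7.4, protocol 10.2 and SAP 6.3: subjects whose first rescue date is before the Visit 8 (Week 24) date are excluded from the PPS; therapy started on or after Visit 8 does not affect membership. Use the Visit 8 date, which SAP 6.3 already uses, and not the HbA1c collection date, so that a missing sample does not break the rule.
2. In protocol 7.4, keep the 8.5% line as clinical guidance, but state that therapy started on the Week 24 value is post-study care and does not count as rescue for the PPS. Striking only the timing words would be wrong: entry allows HbA1c from 7.0% to below 11.0%, so an undated limit could be met at baseline.
3. In SAP 20.1.4, 20.1.6 and 20.1.8, set a value to missing only when rescue started before that sample's collection date.

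The cost is one sentence in three places, one clarification and three date comparisons. The first rescue date, visit dates and collection dates are already collected. The downside is that excluding subjects rescued before Visit 8 still selects to some degree on poor control in the PPS.

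Deleting the 7.4 sentence, so that 10.2 and SAP 6.3 govern, would also be consistent and would avoid that selection. It would leave subjects on added agents, including bolus insulin, in a per-protocol set.

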## **7.5. Preparation/Handling/Storage/Accountability**

The investigator or his or her designee is responsible for

- confirming that appropriate temperature conditions have been maintained during transit for all study treatment received and any discrepancies are reported and resolved before use of the study treatment. The drug product should be stored at room temperature for no more than 28 days or under refrigerated conditions (2°C to 8°C) for long-term storage.
- ensuring that only participants enrolled in the study may receive study treatment and only authorized site staff may supply or administer study treatment. All study treatments must be stored in a secure, environmentally controlled, and monitored (manual or automated) area in accordance with the labeled storage conditions, with access limited to the investigator and authorized site staff.
- the investigator, institution, or the head of the medical institution (where applicable) is responsible for study treatment accountability, reconciliation, and record maintenance (such as receipt, reconciliation and final disposition records).

## 7.6. Treatment Compliance

Subject compliance with study medication will be assessed at each visit of the treatment period. Compliance will be assessed by

- subject's glycemic control
- adherence to the visit schedule
- dosing-titration algorithm
- administration of study insulin, and
- any other parameters the investigator deems necessary.

Deviations from the prescribed dosage regimen should be recorded in the eCRF.

The subject will be considered significantly noncompliant if during the study he or she misses

- more than 3 consecutive days of study medication (full doses), or
- more than 15 cumulative days of study medication (full doses).

Similarly, a subject will be considered significantly noncompliant if he or she is judged by the investigator to have intentionally or repeatedly taken more than the prescribed amount of medication. All such subjects will be considered to have withdrawn from the study. The last observation carried forward (LOCF) replacement of these subjects will be taken under the supervision of Lilly or its designee if the target number of subjects (a minimum of 200) is at risk to be achieved.

## 7.7. Concomitant Therapy

All combination of OAMs or GLP-1 RAs are allowed in the protocol and can be continued with Basaglar. Subjects need to be on GLP-1 RA or at least 2 OAMs at the time of entering the study. For subjects on thiazolidinediones, the investigator may consider reducing the dose or discontinuing it, if there is risk of fluid retention in the subject or complaint of shortness of breath during rest. For subjects on sulphonylureas, the investigator may consider to modify the dose in cases of hypoglycemia.

## 7.8. Treatment after the End of the Study

### 7.8.1. Study Extensions

Not applicable.

### 7.8.2. Treatment after Study Completion

Basaglar will not be made available to subjects from the study team after conclusion of the study. The subject can continue to take commercially available Basaglar or any other basal insulin analog as recommended by the investigator. The access of the drug to the subjects can be confirmed in the follow-up visit.

### 7.8.3. Special Treatment Considerations

Following an event of severe hypoglycemia or in cases where subjects require assistance to recover from hypoglycemia, the subject may continue in the study depending on the decision of the investigator in consultation with Lilly CRP. This may require a reduction in dosage of basal insulin being administered and titration algorithm provided above can be referred to or at the discretion of the investigator.

## 8. Discontinuation Criteria

### 8.1. Discontinuation from Study Treatment

#### 8.1.1. Permanent Discontinuation from Study Treatment

Following are the possible reasons leading to permanent discontinuation of investigational product:

- **Subject decision**
  - The subject requests to discontinue investigational product.
- **Discontinuation due to a hepatic event or liver test abnormality**

Subjects who are discontinued from the investigational product due to a hepatic event or liver test abnormality should have additional hepatic safety data collected in the eCRF.

Discontinuation of the investigational product due to abnormal liver tests **should be** considered by the investigator when a subject meets 1 of the following conditions after consultation with the Lilly-designated medical monitor:

  - alanine aminotransferase (ALT) or aspartate aminotransferase (AST)  $>8X$  upper limit of normal (ULN)
  - ALT or AST  $>5X$  ULN for more than 2 weeks
  - ALT or AST  $>3X$  ULN and total bilirubin level (TBL)  $>2X$  ULN or international normalized ratio  $>1.5$
  - ALT or AST  $>3X$  ULN, with the appearance of fatigue, nausea, vomiting, right upper-quadrant pain or tenderness, fever, rash, and/or eosinophilia ( $>5\%$ )
  - alkaline phosphatase (ALP)  $>3X$  ULN
  - ALP  $>2.5X$  ULN and TBL  $>2X$  ULN
  - ALP  $>2.5X$  ULN, with the appearance of fatigue, nausea, vomiting, right quadrant pain or tenderness, fever, rash, and/or eosinophilia ( $>5\%$ )

Subjects discontinuing from the investigational product prematurely for any reason should complete adverse events (AEs) and other safety follow-up as per Section 2 (Schedule of Activities), Section 9.2 (Adverse Events), and Section 9.4 (Safety) of this protocol.

